7.1.2.3 Exploratory Efficacy Endpoints

10

A large black rectangular redaction box covers the majority of the page content, starting below the header and ending above the footer. The redaction is approximately 85% of the page width and 80% of the page height.

[REDACTED]	[REDACTED]

[REDACTED]

A series of 15 horizontal black bars of varying lengths, decreasing in size from left to right. The bars are evenly spaced and extend across the width of the frame. The lengths of the bars decrease in a regular, linear fashion from the longest bar on the far left to the shortest bar on the far right.

[REDACTED]

[REDACTED]

[REDACTED]

[REDACTED]

1

[REDACTED]
[REDACTED]
[REDACTED]
[REDACTED]
[REDACTED]
[REDACTED]
[REDACTED]
[REDACTED]-Responder".

*Step1 of the new Revised CRISS is same as that of Revised CRISS.

7.1.3 Safety Assessments

7.1.3.1 Adverse Events

All AEs and SAEs will be recorded in the source documents. All AEs and SAEs that occur from the time written informed consent is obtained until the end of the Safety Follow-up Period (4 weeks after the last treatment visit, for safety monitoring) will be recorded in the eCRF.

An AE is any untoward medical occurrence in a subject or clinical investigation subject administered a pharmaceutical product that does not necessarily have a causal relationship with this treatment.

Adverse events will be coded according to the MedDRA version 25.0 or higher.

(1) Treatment Emergent Adverse Events/ Treatment Emergent Serious Adverse Events (TEAEs/TESAEs)

Protocol definition

AEs will be classified as 'treatment-emergent' if they arise following the first administration of study drug in the double blind treatment period (after randomization) or if a predose AE increases in severity following dosing in the double blind treatment period (after randomization).

Analysis rule to determine TEAE using onset date of AEs

An AE is classified as treatment emergent if it newly occurred on or after the first dose of study drug. According to this data handling, for the severity part in the above TEAE definition, the AE with upgraded severity and with the new onset date during the treatment period will be

automatically included as TEAE.

If the AE start date is incomplete, it will be imputed as follows for the purpose of determining TEAE and AE duration:

- If the start date is completely missing, the start date will be equal to the date of the first dose date of study treatment. However, if the stop date is not missing and is before the date of the first dose of study treatment, then the stop date will be used instead of the start date and the AE will not be considered as TEAE.
- If the start date is missing, but the month and year are not missing and are equal to the month and year of the first study dose, then start date will be equal to the date of the first dose date of study treatment. If the month of the start date is not equal to the month of the first study dose, then start date will be equal to the first date of the month of the start date. these events will be considered as TEAE.
- If the start date and month are missing, then the first day of the first month (January) will be used.

If an AE stop date is incomplete, it will be imputed as follows for the purpose of determining TEAE and AE duration:

- If the AE stop date is completely missing, then the stop date will be equal to the subject's last observed date.
- If the stop date is missing, but the month and year are not missing and are equal to the month and year of the last observed date, then stop date will be equal to last observed date. If the month of the stop date is earlier than the last observed month, then stop date will be equal to last day of the month of the stop date.
- If the stop date and month are missing, then the last day of the last month (December) will be used.
- If the AE stop date is prior to the date of the first dose date of study treatment, the AE will not be considered as TEAE.

(2) Adverse Drug Reaction

A TEAE is considered "adverse drug reaction" if it has been assessed as having a "reasonable possibility" in relationship to the study drug.

(3) Serious Adverse Events

A serious Adverse Event (SAE) is defined as any untoward medical occurrence that at any dose:

- Results in death;
- Is life-threatening;

- Requires hospitalization or prolongation of existing hospitalization;
- Results in persistent or significant disability or incapacity;
- Is a congenital anomaly or birth defect;
- Is an important medical event;

(4) Trial Emergent Adverse Events

An AE is considered “Trial Emergent Adverse Events” if it occurred before the first dose of study drug at Day 1.

(5) Duration of Adverse Events

Duration of the AE and time to the AE occurrence from start of study treatment will be calculated and presented in days.

- Duration of Adverse Events (days) = AE stop date – AE start date + 1,
- Time to AE onset (days) = AE start date – The first administration date of study drug + 1

(6) AESI

One AESI that will be considered during this study includes hepatic AESIs, defined as

- Clinically significant liver dysfunction, as follows:
 - ALT or AST $> 8 \times$ ULN
 - ALT or AST $> 5 \times$ ULN for more than 2 weeks
 - Elevated total bilirubin $> 2 \times$ ULN and ALT or AST $> 3 \times$ ULN, or
 - Symptoms consistent with liver dysfunction (e.g., fatigue, nausea, vomiting, abdominal pain or tenderness, fever, rash, eosinophilia $> 5\%$) with concomitant ALT or AST values $> 3 \times$ ULN.
- Hepatic AEs or hepatic laboratory abnormalities that lead to study drug interruption or discontinuation (see protocol).
- Any other laboratory or clinical abnormality that Sponsor Medical Monitor and/or Investigator considered as significant.

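### Read literally, the SAP's missing-day rule labels an ongoing adverse event from a month before first dose as treatment-emergent

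*SAP*

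**What the plan says.** SAP 7.1.3.1 (1) gives the governing rule: "An AE is classified as treatment emergent if it newly occurred on or after the first dose of study drug". A pre-dose event that worsens on treatment is covered there too, because it is entered with a new onset date.

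For a start date with a missing day, the same section has two branches.

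- Month and year "equal to the month and year of the first study dose, then start date will be equal to the date of the first dose": the event becomes a TEAE starting on the day of first dose.
- "If the month of the start date is not equal to the month of the first study dose, then start date will be equal", and the imputed day is the first of that month. This branch closes with the statement "these events will be considered as TEAE".

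Two stop-date provisions bear on this. One is an exclusion: "AE stop date is prior to the date of the first dose date of study treatment, the AE will not be considered as TEAE". The other, which begins "If the AE stop date is completely missing, then the stop date will be equal to the", names that subject's last observed date.

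SAP 7.1.3.1 (4) has a separate class, the Trial Emergent Adverse Event, for an AE "if it occurred before the first dose of study drug at Day 1". SAP 8.3.1 lists that class on its own. Protocol 14 likewise classes events before administration as baseline events, and Protocol 16.3.5.1 defines TEAEs by onset or worsening on or after first dose. SAP 1 states that its analysis details override the protocol's.

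**The concern.** The second branch tests only whether the months differ. For a later month, that is harmless. For an earlier month, the recorded month already shows that the event began before any study drug, yet the rule imputes a pre-dose date and then calls the event treatment-emergent. The same event would qualify for both the Trial Emergent listing and the TEAE tables.

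Such events can exist in the database: AEs are recorded from informed consent (SAP 7.1.3.1) and screening lasts up to 28 days (SAP 3.2.1).

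What is at stake is the accuracy of the TEAE tables in a small trial. With 36 subjects per arm, one subject is 1/36 = 2.8%. A second subject with the same preferred term makes 2/36 = 5.6%, which passes the 5% threshold for the frequent-TEAE table in SAP 8.3.1. A large negative onset day attached to a TEAE would also need explaining in the study report.

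**Working it through.** The plan gives no figure to reproduce, so the check applies the rule to test dates and then bounds its reach.

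**1. The rule on test dates.** Take first dose as 10 Mar 2021 (illustrative). SAP 7.1.3.1 (5) gives time to onset = AE start − first dose + 1.

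| Recorded start | Stop | Imputed start | Onset day | Label under the rule |
|---|---|---|---|---|
| Feb 2021 | ongoing | 1 Feb 2021 | −37 + 1 = −36 | TEAE |
| Feb 2021 | 1 Mar 2021 | 1 Feb 2021 | −36 | not TEAE (stop-date exclusion) |
| Feb 2021 | Mar 2021, day missing, set to 31 Mar* | 1 Feb 2021 | −36 | TEAE |
| Mar 2021 | ongoing | 10 Mar 2021 | 0 + 1 = 1 | TEAE |
| May 2021 | ongoing | 1 May 2021 | 52 + 1 = 53 | TEAE (correct) |
| Mar 2022 | ongoing | none | none | fits neither branch |

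*If the subject's last observed month is later than March.

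Rows 1 and 3 are the fault. Had the February event carried a complete date, any day in February would have made it not a TEAE under the governing rule. Losing the day reverses the classification even though the timing relative to first dose is not in doubt. The stop-date exclusion cannot catch row 1, because a missing stop date becomes the last observed date.

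The last row is a separate small gap. The first branch compares month and year, but the second compares month only. An event in the same calendar month one year on is possible, because follow-up runs to Day 393.

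**2. Size of the negative onset day.** The imputed date is the first of an earlier month. The smallest possible distance is from 1 Feb to a first dose on 1 Mar in a non-leap year, which is 28 days. The onset day is then −28 + 1 = −27, and in every other case it is −27 or lower.

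**3. Upper bound on reach.** Assume a screening period of L days, onset uniform over it, and first-dose day D uniform over a 30-day month. The share of screening days in an earlier month is (L + 1 − D)/L for D = 1 to L, and zero otherwise. Summing over D gives (L + 1)/2, and dividing by 30 gives the average.

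- L = 28: 14.5/30 = 48%
- L = 14: 7.5/30 = 25%
- L = 7: 4/30 = 13%

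A direct count over every first-dose date in 2021 with a 28-day screening gives 47.7%, in agreement. These are shares of all screening-period AEs. An affected AE must also have a missing start day and an actual or imputed stop on or after first dose. The documents give neither proportion.

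**The case against.** The strongest reply is that the literal reading is not the intended one. The bullets say that they impute dates for determining TEAE status and duration, so they could be taken merely to feed the governing onset rule. On that reading, an event imputed to 1 Feb with first dose on 10 Mar is not a TEAE. The closing sentence has no clear antecedent and may have been meant only for the first-dose month and later ones. That is plausible, but the text does not say so. The sentence follows directly on the branch for differing months and assigns a status, so a programmer could reasonably code it as written.

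There are also safeguards. SAP 7 lets the blinded data review meeting override the conventions. Onset date is an AE form field (Protocol 14.7), data are queried (Protocol 15.2 and 15.4), and pre-existing illness is medical history unless it worsens (Protocol 14.7). These shrink the pool of affected events and stand as a limit on size. None of them supplies a correction.

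It may also be said that counting partial dates as treatment-emergent is conservative. That holds where timing is uncertain, as in the first-dose-month branch. It does not hold where the known month settles the question.

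A reader might infer that the serious TEAE and drug-reaction tables are contaminated as a matter of course. The documents do not support that. Entry needs a serious classification or a reasonable-possibility assessment as well, and an event known to precede any dose would not ordinarily be assessed as related.

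**Conclusion.** The point holds on the text. A day-missing AE from a month before first dose, still ongoing at first dose or with an imputed stop on or after it, is classed as a TEAE against the SAP's own onset rule and its own pre-dose category. This is a stated rule that gives a wrong classification, not an omitted detail.

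The consequence is minor. The number of such AEs is unknown and probably very small. The rule is identical in both arms, so it adds misclassified events rather than an evident bias towards one arm. Efficacy is untouched.

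Two stronger readings should be resisted. It does not follow that all screening AEs become TEAEs, because those with complete dates are classed correctly and those that ended before first dose are excluded. Nor is 48% the share of AEs affected. It is the upper end of a range that falls to about 13% for a 7-day screening, and it comes before the two further conditions are applied. The range rests on uniform onset and uniform first-dose day.

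**What to change.** Replace the second branch of the missing-day rule in SAP 7.1.3.1, comparing month and year together:

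- **Earlier than the first-dose month and year:** impute the first of that month, so that duration can still be calculated, and class the event as pre-dose, not TEAE.
- **Equal:** impute the first-dose date; TEAE unless the stop date is before first dose.
- **Later:** impute the first of that month; TEAE.

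Comparing the year as well also closes the gap for the same calendar month one year later. The cost is a short rewording in the SAP and one condition in the AE derivation, made before database lock. No additional data are needed.

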7.1.1.4 Prior or Concomitant Medication

Medications will be coded according to the WHO Drug Dictionary (WHO-DD) B3 MAR 2019 version or higher.

(1) Prior Medication

Any prior medication, including prescription and over-the-counter medications, taken within 30 days before screening and all SSc-related medications used since diagnosis will be recorded on the eCRF and source documents. The following information will be collected: name of medication, dose, duration, and reason for use.

(2) Concomitant Medication

Concomitant medication(s) is defined as any medication, other than study drug, which is taken during the treatment period, including prescription, over-the-counter medications, herbals, dietary supplements, and recreational drugs. All concomitant medication(s) taken while the subject is participating in the study will be recorded.

Concomitant medication(s) will be provided only if deemed necessary by the Investigator or the subject's personal physician.

Analysis rules to determine prior medications and concomitant medications

Medications with a stop date before the first date of study drug dosing will be defined as prior medications. Medications with start date or stop date on or after the first date of study drug dosing or ongoing up to week 56 will be defined as concomitant medications.

If the medication start date is incomplete, then it will be imputed as follows for the purpose of determining concomitant use:

- If the start date is completely missing, the start date will be equal to the first dose date.

However, if the stop date is not missing and is before the first dose date, then the stop date will be used instead of the start date. It will not be considered as concomitant medications.

- If the start date is missing, the first day of the month will be used.
- If the start date and month are missing, then the first day of the first month (January) will be used.

If the medication stop date is partial, then it will be imputed as follows for the purpose of determining concomitant use:

- If the stop date is completely missing and the medication is not ongoing, the stop date will be equal to the last dose date or date of completion/withdrawal, whichever is the latest.
- If the stop date is missing, the last day of the month will be used.
- If the stop date and month are missing, then the last day of the last month (December) will be used.

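### An AE start date known only to the year is set to 1 January with no check against first dose, so an on-treatment AE in the first-dose year is classed as pre-dose

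*SAP*

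**What the plan says.** SAP 7.1.3.1 classes an AE as treatment-emergent by its onset date: on or after first dose. Incomplete start dates are imputed "for the purpose of determining TEAE and AE duration", so the imputed date decides the class. The start-date rules are:

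- **Wholly missing:** "If the start date is completely missing, the start date will be equal to the date of the first dose date of study treatment". If a known stop date falls before first dose, the stop date replaces the start and the event is not a TEAE.
- **Day missing, month and year known:** first-dose date if the month and year match first dose, otherwise the first of the known month. This bullet ends "these events will be considered as TEAE".
- **Day and month missing:** "If the start date and month are missing, then the first day of the first month (January) will be used". First dose and the stop date are not mentioned.

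A later bullet, beginning "If the AE stop date is prior to the date of the first dose date of study treatment", removes TEAE status. No bullet restores it. An AE goes to the separate trial-emergent class "if it occurred before the first dose of study drug at Day 1". Collection covers "All AEs and SAEs that occur from the time written informed consent is obtained", so genuine pre-dose AEs do exist in the database.

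The protocol gives no rule for partial AE dates, and SAP Section 10 lists no change on this point.

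**The concern.** The year-only rule is the only one of the three that can place an event before first dose when nothing in the record says it happened then. For any first dose after 1 January, a year-only start in that year always lands before dosing. Knowing the year thus makes an AE less likely to be counted than knowing nothing, which runs against the inclusive direction of the wholly missing rule.

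Most of the AE summaries in SAP 8.3.1 rest on TEAE status, and SAP 7.1.3.1 defines adverse drug reactions as a subset of TEAEs. A misclassed event therefore leaves those tables as well and appears in the trial-emergent listing as if it preceded treatment. The imputed date also lengthens the AE's duration and makes time to onset zero or negative.

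**Working it through.** The plan states no figure on this point, so there is none to reproduce. The check applies the SAP 7.1.3.1 rules literally.

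**1. The rules applied to one event.** Assume first dose on 15 March 2022, true onset on 20 June 2022 and stop on 1 July 2022. The SAP defines time to onset = start − first dose + 1.

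| Start as recorded | Imputed start | Time to onset (days) | Class |
|---|---|---|---|
| 20 June 2022 | none needed | 98 | TEAE |
| June 2022 | 1 June 2022 | 79 | TEAE |
| Wholly missing | 15 March 2022 | 1 | TEAE |
| 2022 only | 1 January 2022 | −72 | Not TEAE |

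Only the year-only record gets the wrong class, although its stop date shows that the event continued after dosing. A start recorded only as 2023 becomes 1 January 2023 and is correctly a TEAE. A first dose on 1 January also causes no error.

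**2. Duration.** The SAP defines duration = stop − start + 1. Take first dose on 15 June and an AE from 1 to 10 September, with its start recorded as year only. The true duration is 10 days. Under the current rule it is 1 January to 10 September = 253 days. With the first-dose date it is 15 June to 10 September = 88 days. SAP 8.3.1 names no duration table.

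**3. How often the rule would be wrong when it applies.** Assumptions, none from the documents: onset equally likely on each day, consent 28 days before Day 1 (the longest screening in SAP 3.2.1), follow-up to Day 393 (nominal Week 56) and a non-leap year. Among year-only AEs in the first-dose year, the misclassed share is on-treatment days in that year ÷ (screening + on-treatment days in that year):

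- 15 January: 351/(14 + 351) = 96.2%
- 15 June: 200/(28 + 200) = 87.7%
- 1 October: 92/(28 + 92) = 76.7%
- 4 December: 28/(28 + 28) = 50.0%
- 15 December: 17/(28 + 17) = 37.8%
- All first-dose dates from 2 January to 31 December, equally weighted: 66,430/76,244 = 87.1% (93.0% with 14-day screening)

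With a wider denominator, all year-only on-treatment AEs in either calendar year over 365 equally likely first-dose dates, the misclassed share is 66,430/(365 × 393) = 66,430/143,445 = 46.3%. The remainder start in the following year, apart from those with a 1 January first dose, and are classed correctly.

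**4. Size per event.** SAP 3.3 plans 36 subjects per arm. One subject is 1/36 = 2.8 percentage points. A preferred term seen in 2/36 = 5.6% of MT-7117 subjects that loses one falls to 2.8% and leaves the table of TEAEs at 5% or more.

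**5. The same wording for medications.** SAP 7.1.1.4 uses the same 1 January sentence. There it is harmless, because "Medications with start date or stop date on or after the first date of study drug dosing" count as concomitant: a stop date on or after first dose settles the class. AE status has no such test.

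**The case against.** The strongest objection is that the rule will rarely be used. AEs are asked about at every visit (Protocol 14.7), and nominal visits, counting the telephone visits, are at most 70 days apart (Protocol Table 1). The AE form records the onset date, and discrepancies go back to the site (Protocol 15.2 and 15.4). SAEs and hepatic AESIs are due within 24 hours of awareness (Protocol 14.8), so an unknown month is least likely for the events that matter most. The liver-threshold tables use laboratory values, not AE dates. The blinded data review may depart from any convention in SAP Section 7, and the event stays in the all-AE listing. All of this stands, and it limits the effect. It does not make the default rule right, and no check for this case is prespecified.

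It is also fair that the percentages in the working are not rates of misclassified AEs. They are shares of a set whose size is unknown, under an assumed uniform onset. The duration example is contrived too, since a stop date known to the day rarely goes with an unknown onset month.

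A third objection concerns the remedy. Simply moving every such start to first dose would break some records. With first dose on 15 June and stop on 1 June, the duration would be 1 June − 15 June + 1 = −13 days, and the event would be neither a TEAE nor, by its imputed date, pre-dose. This is correct, so the fix needs a stop-date clause.

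**Conclusion.** The rule is wrong as written. For any first dose after 1 January, an on-treatment AE with a year-only start in the first-dose year is classed as pre-dose, and nothing in the SAP or protocol restores it. This follows from the text alone and needs no assumption. True screening AEs and year-only starts in the following year are classed correctly.

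The overall effect cannot be estimated, because the number of year-only AE dates is not given. It is probably very small, so this is a minor correction. A reader might infer from the 87% figure that the TEAE tables miss a large part of the adverse events, or that the comparison between arms is biased. The documents support neither: the figure is a share of a probably tiny set under assumed uniform onset, and the rule is identical in both arms.

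**What to change.** Replace the year-only bullet in SAP 7.1.3.1 with the following:

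- If the AE start day and month are missing and the year equals the first-dose year, set the start to the first-dose date.
- If the stop date, imputed where necessary, is before first dose, do not use the first-dose date. Keep 1 January, or use the stop date as the start as the wholly missing rule does, and do not class the AE as a TEAE.
- For all other years, keep 1 January.

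An optional clarification: state that the closing sentence of the day-missing bullet does not cover a known start month before the first-dose month, since its reach is ambiguous.

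The cost is one line of derivation code and a short SAP edit. A few year-only screening AEs would become TEAEs if they are still ongoing at first dose or have a year-only stop imputed to 31 December. This would be more common with late-year first doses: under the same assumptions, 28/45 = 62% of year-only AEs in the first-dose year are screening events when first dose is 15 December, although only those two kinds would change class. That error is in the conservative direction the SAP already accepts for wholly missing dates.

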8.1.6 Prior or Concomitant Medications

The prior and concomitant medications will be summarized in table separately by ATC level 2, preferred name and treatment group and presented in data listing for the SAF population.

Regarding of the concomitant medication, the dosage of the following medications which is ongoing at the time of the first dose of study drug or is started after the first dose of study drug will be descriptively summarized. Also, the duration of the medication use will be descriptively summarized. Data describing units other than "mg" or "g" will be included only in the tabulation of time period. These medication codes is attached in the Appendix 13.1. For "METHYLPREDNISOLONE" and "METHYLPREDNISOLONE SODIUM SUCCINATE", the dose multiplied by 0.8 will be used for tabulation to convert these drugs to equivalent doses of corticosteroid.

Mycophenolate (up to 3g/day)

Mycophenolic acid (up to 2.14 g/day)

Methotrexate (up to 25 mg/Week)

Leflunomide (up to 20 mg/day)

Azathioprine (up to 3 mg/kg/day)

Corticosteroid (up to \leq 40 mg/day of prednisone)

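### An AE stop date known only to the final year of observation is set to 31 December with no cap, so the AE duration can run past the subject's last observed date

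*SAP*

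**What the plan says.** SAP 7.1.3.1 gives a set of rules for incomplete AE stop dates and states their purpose: "If an AE stop date is incomplete, it will be imputed as follows for the purpose of determining TEAE and AE duration".

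- Wholly missing: "If the AE stop date is completely missing, then the stop date will be equal to the subject's last observed date".
- Month and year known: if they match "the month and year of the last observed date, then stop date will be equal to last observed date". If the month is earlier than the last observed month, the end of that month is used.
- Only the year known: "If the stop date and month are missing, then the last day of the last month (December) will be used". No condition on the last observed date is attached.

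The same section defines duration as stop date minus start date plus 1 and says: "Duration of the AE and time to the AE occurrence from start of study treatment will be calculated and presented in days".

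For medications, SAP 7.1.1.4 has a year-only stop rule in the same words, and its month-known rule also has no cap. The stated purpose is narrower: "If the medication stop date is partial, then it will be imputed as follows for the purpose of determining concomitant use". A wholly missing stop for a medication that is not ongoing has a different anchor: "the stop date will be equal to the last dose date or date of completion/withdrawal, whichever is the latest". SAP 8.1.6, on the listed immunosuppressants and corticosteroid, then says: "Also, the duration of the medication use will be descriptively summarized". It does not say which stop date that duration uses.

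**The concern.** The first two AE rules show the intent that an imputed stop should not fall after observation of the subject has ended. The year-only rule omits that limit. If the site records only the year, and that is the year in which the subject was last observed, the event is extended to 31 December however early in the year observation ended. The extra days then enter a quantity that the SAP says will be calculated and presented.

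In that situation the ordering is also perverse: a record with the year known is given a longer duration than a record with nothing known. At stake is the credibility of individual AE durations, not any test or estimate of efficacy.

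**Working it through.** The documents give no figure for this point, so there is nothing to reproduce. The check applies the SAP rules to the calendar.

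**Inputs from the documents.** The three AE stop rules and the duration formula (SAP 7.1.3.1); scheduled end of observation at Week 56, Day 393 (SAP 7.2).

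**Size of the overrun.** Let L be the last observed date.

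- Recorded year equal to the year of L: overrun = 31 December − L. This runs from 0 days (L = 31 December) to 364 days (L = 1 January), or 365 in a leap year. For L = 31 March 2022 it is 275 days.
- Recorded year earlier than the year of L: 31 December of that year lies before L, so there is no overrun, and the imputed stop is nearer the true stop than L would be.

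**Worked examples.** Assumed: L = Day 393 = first dose + 392 days; AE start = L − 27 days; stop recorded only as 2022.

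| First dose | L | AE start | Duration, stop wholly missing | Duration, year only | Days past L | Duration with cap |
|---|---|---|---|---|---|---|
| 15 Jan 2021 | 11 Feb 2022 | 15 Jan 2022 | 28 | 351 | 323 | 28 |
| 1 Jun 2021 | 28 Jun 2022 | 1 Jun 2022 | 28 | 214 | 186 | 28 |
| 20 Nov 2021 | 17 Dec 2022 | 20 Nov 2022 | 28 | 42 | 14 | 28 |

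In each row the year-only duration equals 28 plus the overrun; for the second row, 28 + 186 = 214.

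**How often the final year would be the recorded one.** This is illustrative only. Assume one first dose on each day of 2021, L = Day 393, and a true stop equally likely on any of Days 1 to 393. L then falls once on each day of the year. If L is day d of its year, d of the 393 possible stops lie in that final year.

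- Share of stops in the final year = mean of d / 393 = 183 / 393 = 46.6%.
- Mean overrun among those = 365 − (Σd² / Σd) = 365 − (2 × 365 + 1)/3 = 365 − 243.7 = 121 days.
- Against the wholly-missing rule, year-only is worse in 46.3% of cases, better in 53.4% and equal in the rest.
- Mean of imputed minus true stop: 196.0 days (wholly missing), 182.0 days (year only as written), 125.5 days (year only with cap). The last follows from the others: 182.0 − 0.466 × 121.3 ≈ 125.5.

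**Effect on classification.** SAP 7.1.3.1 removes treatment-emergent status only when the stop precedes first dose. For a dosed subject the last observed date cannot precede first dose, so neither the late date nor the cap changes that status.

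**The case against.** Several stronger readings are tempting, and the documents do not support them.

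- A reader might infer that knowing the year is always worse than knowing nothing. It is so only when the recorded year is the final observed year. For earlier years the rule does better, and in the enumeration its mean error is smaller overall (182.0 against 196.0 days).
- A reader might infer that mean AE durations, for example of hepatic or hyperpigmentation events, will be distorted. SAP 8.3.1 lists no mean or table of AE duration; a listing would satisfy the statement that duration is presented.
- A reader might infer that immunosuppressant and steroid durations are wrong. The medication imputation is stated only for classifying concomitant use, where a late stop does no harm. Its use in SAP 8.1.6 is plausible, since no other stop-date rule is given, but it is not stated.
- Averaging 31 December minus L over evenly spread last observed dates gives about 182 days. That ignores that a subject last seen early in a year has few days in that year on which an event could stop; weighting for this gives 121 days.

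Other points carry some weight. The introduction to SAP section 7 lets the blinded data review meeting override these conventions, so an absurd date could be corrected; but it supplies no cap. Protocol 14.7 collects the date of resolution, so year-only stops may be rare. Protocol 14.9 follows AEs until they resolve or stabilise, and the visible SAP does not define the last observed date. If that term means the last visit, a true stop after it is possible, and calling every such date impossible would go too far.

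What stands against the plan is narrow: a stated rule, followed as written, gives a stop date that its neighbouring rules would not allow.

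**Conclusion.** The point holds for AE stop dates known only to the year, when that year is the one in which the subject was last observed. The range of 0 to 364 days (365 in a leap year) follows from the rule alone. The 46.6% share and the 121-day mean overrun rest on the assumed uniform dates and on Day 393 as the end of observation, and should not be read as predictions. The frequency of year-only stops is unknown.

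The consequence is limited to presented AE durations. Treatment-emergent status, incidence tables, efficacy and power are untouched. For medications the matter is a request for clarification, not a demonstrated error. This is a minor correction, worth making because it is simple and removes an inconsistency within one section.

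**What to change.** In SAP 7.1.3.1, replace the year-only stop rule with: *if only the year is known, use the earlier of 31 December of that year and the subject's last observed date.* It would help to state what the last observed date means, and whether it includes AE follow-up contacts, since the existing rules already depend on it.

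In SAP 8.1.6, state which stop date the medication durations use. If it is the date imputed under 7.1.1.4, add the analogous cap there with that section's own anchor: the later of the last dose date and the date of completion or withdrawal.

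The cost is one clause for AEs and a sentence or a clause for medications. The AE cap moves only imputed stops that fall after the last observed date. If that date is defined as the last visit, the cap could shorten an event that truly ended later, which is the reason to define it.
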